14.10 Insurance

The Sponsor of this study, the Institute of Tropical Medicine has obtained a (no-fault) study insurance to cover any injury, damage or loss to study participants and which is caused directly or indirectly by their participation in the study.

14.11 Access to the Study Data by KCE and similar institutes in the EU

This section should be read in conjunction with the research agreement, which supersedes the protocol in case of contradictory statements.

A distinction is to be made for access by KCE (and similar institutes in Europe) and access by other parties.

Access to Study Data by KCE is fully defined in the contract between KCE and the Sponsor and the research agreement template is publicly available on the KCE website. Link: <https://kce.fgov.be/en/resources-for-investigators>

14.12 Access to the final trial dataset by other parties

After study completion and publication of results, anonymized or pseudonymized individual participant data may be shared by means of a managed access procedure. To this end, the ITM Data Sharing Policy will be adhered to. Access requests will be reviewed and approved prior to release by ITMs Data Access Committee. Requests for access can be made centrally through: <https://www.itg.be/E/data-sharing-open-access>.

15 DISSEMINATION POLICY

15.1 Dissemination policy

Following finalization of the end of study report, the study results will be disseminated as soon as possible. Particular efforts will be made to communicate the study results to those who participated in the design and conduct of the study. This will include SENSOA, SCIENSANO, RIZIV/INAMI, Cavaria, Boys Project and Roze Huis. Pamphlets with the key study findings will be prepared and made available to participants and others in all PrEP waiting areas in all participating centres.

The final study report will be made available for review and comment by KCE before dissemination if this is required by the agreement KCE. The TSC will develop a study publication plan which will adhere to the following principles:

- Publications follow the 'European Code of Conduct for Research Integrity'
- All publications will acknowledge KCE's funding of the study and as appropriate carry a KCE disclaimer.
- Open access journals will be preferred
- The Consort Guidelines will be followed: <http://www.consort-statement.org/>

The trial will also be registered in the public registry ClinicalTrials.gov prior to the start of enrolment.

15.2 Authorship eligibility guidelines and any intended use of professional writers

The TMG written Study Publication plan will be guided by the ITMs 'Guidelines regarding authorship in scientific publications' document. A key component of this document is that it adheres to the following criteria for authorship:

The basic criterion for authorship is a significant intellectual contribution to the work reported. This contribution has to include at least one of the following points:

- conceptualization of (part of) the work;
- design of the study;

- execution of the study;
- data analysis;
- data interpretation;
- a part in the writing of the article;
- critical revision of the article for content.

It is up to the authors to agree what contribution was significant. In case no consensus is reached then the senior researcher can have a decisive role in the decision.

As a general principle group authorship will be promoted and at least one individual from each participating centre should be an author on all papers.

1. RISK ASSESSMENT OF THE TRIAL INTERVENTION(S)

Risks associated with trial interventions

- A ≡ Comparable to the risk of standard medical care
- B ≡ Somewhat higher than the risk of standard medical care
- C ≡ Markedly higher than the risk of standard medical care

Justification:

As outlined more fully above in section 2, the non-screening arm may have a higher incidence of symptomatic Ng and or Ct infections. There might also be more onward transmission of Ng/Ct to partners.

What are the key risks related to therapeutic interventions you plan to monitor in this trial?

How will these risks be minimised?

Intervention	Body system/Hazard	Activity	Frequency	Comments
Not screening	Increased symptomatic Ng/Ct infections	DSMB Monitoring	Once 50% and 100% of month 6 visits completed	
Not screening	Increased transmission of Ng/Ct	DSMB Monitoring	Once 50% and 100% of month 6 visits completed	

We plan to set up a Data and Safety Monitoring Board (DSMB) within the Trial Steering Committee (TSC) to evaluate if the non-screening arm has an unacceptably high incidence of symptomatic Ng/Ct. This DSMB will include two independent STI experts (Infectious Disease Physicians/Epidemiologists) and the study statistician who will together decide what threshold they determine to be an unacceptable risk and what methodology to use to evaluate this risk.

The DSMB will evaluate the incidence of symptomatic Ng + Ct in both arms once 50% and 100% of individuals have completed their 6 month visit. If the incidence of symptomatic Ng + Ct in the non-screening arm is more than two-fold higher than the screening arm at either of these time points, then serious consideration should be given to stopping the study

For the reasons described above, no safety reporting will be performed besides the reporting of STIs for all participants for the whole duration of the trial.

Since this trial is not considered as a clinical trial according to European Regulation, there will be no submission of the trial documents to the FAMHP.

2. AUTHORISATION OF PARTICIPATING SITES

Appendix 2.1. Required documentation

The following documents will be requested from each of the five participating sites before study initiation:

- CV of the Principal Investigator (PI)
- Final feasibility report

Appendix 2.2. Procedure for initiating/opening a new site

Before a site can start enrolment of participants, a site initiation visit (SIV) will be performed by the sponsor.

The SIV will be performed by the monitor. The monitor will preferably be accompanied by one of the sponsor researchers of the study. The sponsor's data manager will provide training on the electronic CRF database, but this task can also be performed by the study monitor. Only after the SIV for a specific site has taken place and after approval of the monitor – in agreement with the sponsor researcher(s) – the study can be started at this site.

At least the following activities will be carried out by the monitor during the SIV and documented in the SIV report:

- Ethical and GCP requirements: The monitor will meet all the site Investigators and relevant study staff to verify that they have sufficient understanding of the study protocol, procedures and the related GCP requirements.
- Protocol and Case Report Form (CRF) review: The monitor will review the protocol and the eCRF, as well as all the study SOPs, forms and other essential documents, with all the Investigators and relevant study staff.
- The participant flow and screening and recruitment strategies will be discussed so that potential bottlenecks or other problems can be identified and anticipated.
- Investigator file (IF): The monitor will provide the documents for the IF, review them with the site Principal Investigator (PI) and relevant study staff, and discuss the further management.
- Visit of site facilities: The monitor will visit the study site facilities, to confirm that they are adequate for performing key clinical, laboratory and data management activities.
- Communication: The monitor and the site Investigator(s)/site staff will agree on clear communication lines, so that the site Investigator(s)/site staff can contact the monitor and any concerned members of the TSC/TMG any time in-between two visits, for clarification or resolution of additional questions and/or ongoing problems.

Appendix 2.3. Principal Investigator responsibilities

The PI of every participating site will have the following responsibilities:

- Attend the Site Initiation Visit and make sure they are available for discussion during the Site Monitoring Visits and Close-Out Visit
- Ensure that all participating staff are adequately trained in the study protocol and study procedures and have up to date GCP and/or GCLP training as appropriate

- Ensure that the Investigator Site File (ISF) is accurately maintained
- Ensure that all important safety or trial-related information is disseminated timely to all stakeholders within their site

3. SAFETY REPORTING FLOW CHART

All episodes of symptomatic Ng/Ct will be reported as described above in the eCRF and will be discussed at after the two evaluations by the DSMB.

4. AMENDMENT HISTORY

Amendment No.	Protocol version no.	Date issued	Author(s) of changes	Details of changes made
1	2.1	28 Apr 2021	[name]	ICF procedure for qualitative study adapted and possibility of online FGDs added. Adaptation of section 8.12 withdrawal criteria

Statistical Analysis Plan

Efficacy of screening STIs in MSM

GonoScreen

Date: 01 June 2021

Author: [name]
Biostatistician, Institute of Tropical Medicine, Antwerp, Belgium

Approved by: Coordinating Investigator
[name]

Date: ____ / ____ / ____

Table of Contents

1. Introduction.....	2
2. Study design and objectives.....	2
2.1. Study design	2
2.2. Study objectives	3
3. General analysis strategy	3
4. Description of study population.....	3
4.1. Patient accounting	3
4.2. Description of study population	3
5. Description of patient populations and outcomes.....	4
5.1. Patient populations	4
5.1.1. Intention to treat (ITT) analysis	4
5.1.2. Per protocol (PP) analysis.....	4
5.2. Efficacy study endpoints	5
6. Interim analyses	7
7. Analysis of main efficacy outcomes: Incidence of Ng plus Ct.....	7
7.1. Subgroup analyses.....	8
7.2. Other aspects	8
a. Multiplicity	8
b. Missing data	8
8. Analysis of secondary objectives.....	8
8.1. To compare the antimicrobial exposure (ceftriaxone/azithromycin/doxycycline) in the screening and non-screening arms...	8

8.2. To assess if not screening MSM on PrEP for Ng/Ct is non-inferior compared to screening in terms of the incidence rate of symptomatic Ng and Ct infections	8
8.3. To assess the incidence of syphilis.....	9
8.4. To assess the incidence of HIV	9
8.5. To evaluate the economic impact of cessation of Ng/Ct screening in MSM..	9
8.6. To explore PrEP users' perceptions towards STI screening (only for ITM subjects)	9
9. Safety analyses.....	9
10. References.....	9

1. Introduction

This Statistical Analysis Plan (SAP) provides a detailed and comprehensive description of the main, pre-planned analyses for the study “Does screening for gonorrhea and chlamydia affect the incidence of these infections in men who have sex with men taking HIV pre exposure prophylaxis (PrEP): a randomized, multicentre controlled trial”. The purpose of this study is to establish if screening results in a clinically meaningful and cost-effective reduction in Ng/Ct incidence in MSM PrEP cohorts that could outweigh the increased risk of AMR development it confers. The study conduct is described in the Protocol.

These planned analyses will be performed by the statistician(s) at the Clinical Trials Unit of the Institute of Tropical Medicine (Antwerp) in collaboration with the research consortium. The analysis results will be described in a statistical analysis report, to be used as the basis of the primary research publications. This document describes statistical methods for the primary and secondary objectives of the study as defined by protocol. Additional analyses may be performed but are not covered by the current analysis plan.

This analysis plan will be finalized and approved before database lock. Major changes in statistical methodology used for the main and pre-planned analyses from this SAP, will require detailed description and justification in the statistical analysis report. The final analysis datasets, programs, and outputs are archived following good clinical practice guidelines (ICH E9).

2. Study design and objectives

2.1. Study design

This study is a multi-centre, controlled, randomized trial of 3x3 Ng/Ct screening (comparator) vs. no screening (intervention). It will be performed in the PrEP cohorts situated at the ITM, HSP, CHU, UZG and EH. All men in follow up at these five centres who report having had sex with another man in the previous year and are enrolled for PrEP follow up will be eligible to participate in the study. After signing informed consent participants will be randomized via a computer-generated schema to either 3x3 screening or no Ng/Ct screening. In both arms, participants will be followed up in an identical fashion including 3x3 screening. The only difference between the arms will be that in the screening arm, Ng/Ct results will be sent by the STI Laboratory to the

study physicians and these participants will be treated and partner contact tracing will be done. The STI Laboratory will only process the samples/report the results from the non-screening arm at the end of the study. In both arms, all individuals with symptoms compatible with Ng or Ct will be tested and treated for these infections according to current best practice guidelines. At the end of the 12-month study period, participants whose most recent tests were positive for Ng or Ct will receive treatment for these.

2.2. Study objectives

Primary objective:

To assess if not screening MSM on PrEP for Ng/Ct is non-inferior compared to screening in terms of the incidence rate of these infections over a 12-month period.

Secondary objectives:

- 1) To compare the antimicrobial exposure (ceftriaxone/azithromycin/doxycycline) in the screening and non-screening arms
- 2) To assess if not screening MSM on PrEP for Ng/Ct is non-inferior compared to screening in terms of the incidence rate of symptomatic Ng and Ct infections
- 3) To assess the incidence of syphilis
- 4) To assess the incidence of HIV
- 5) To evaluate the economic impact of cessation of Ng/Ct screening in MSM
- 6) To explore PrEP users' perceptions towards STI screening (only for ITM subjects)

3. General analysis strategy

Scheduled visits that were performed out of window (cfr. protocol) are considered as unscheduled visits, with the corresponding scheduled visit considered as 'not done'.

4. Description of study population

The study population will be described overall and in each hospital separately.

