5.1.1. Intention to treat (ITT) analysis

In the Intention-to-Treat analysis, all participants will be analysed according to their randomized allocation, even in case they receive another intervention, show protocol violations prior to or during the study, or are lost to follow-up. The Intention-to-Treat analysis will include all randomized participants with at least one follow-up visit.

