5.1.2. Per protocol (PP) analysis

In the per-protocol analysis only participants who receive intervention as planned, and follow the protocol as planned are included.

In Table 1 the protocol violations are classified as minor and major where minor violations can be included in the PP analysis population and major violations are excluded.

Table 1: The protocol violations classified as minor or major violation

Protocol Violation	Major/Minor Violation	Comments
Inclusion criteria		
1. Able and willing to provide informed consent	Major	
2. Men (born as males) and transwomen aged 18 or more	Major	
3. Has had sex with another man in the last 12 months	Major	
4. Enrolled in Belgian PrEP program at ITM/HSP/EH/CHU/UZG with approval for TDF/FTC (Tenofovir disoproxil fumarate/Emtricitabine) reimbursement from a Belgian Medical Aid	Major	
5. Willing to comply with the study procedures and to attend the clinic for the 3-monthly visits	Major	
Exclusion criteria		
1. Enrolment in another interventional trial	Major	
2. Tests HIV-positive at screening	Major	
3. Symptoms of proctitis or urethritis	Major	
Treatment violations		
1. Not following the randomized intervention (incl. participants who receive test results)	Major	
Follow-up violations		
1. Fewer than three scheduled follow-up visits with Ng/Ct result available	Major	

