5.2. Efficacy study endpoints

Primary endpoint

Incidence of Ng plus Ct detected at any site.

Numerators: Cumulative number of laboratory-confirmed diagnoses of Ng plus Ct in 12 months in screening/non-screening arms. Each participant can only contribute one diagnosis of Ct and one diagnosis of Ng per (scheduled or unscheduled) visit - regardless of number of sites infected. Thus each participant can contribute up to 2 diagnoses (Ct/Ng) at each (scheduled or unscheduled) visit. The numerator includes laboratory-confirmed diagnoses made between scheduled visits, performed inside or outside of the study.

Denominators: Number of scheduled study visits with available results for the diagnosis of Ng/Ct. The denominator does not include unscheduled visits.

The diagnosis of Ng and Ct will be made via nucleic acid amplification testing (NAAT) performed on rectal and pharyngeal swabs and urine.

If the person urgently requires knowing if they are infected with Ng/Ct or not this will be done by repeat testing for these infections. If this test is positive for Ng/Ct then this will be counted as an intervisit infection in the final analysis.

In the primary analysis, the primary endpoint (as described above) includes all Ng/Ct diagnoses. Hence it is implicitly assumed that every diagnosis is a new infection. It is however possible that an Ng/Ct infection detected at the 3 to 12 month visit in the non-screening arm is simply a non-resolved infection from the prior visit. This could spuriously increase the measured incidence in the non-screening group. Because this risk only applies to the non-screening arm it results in a bias towards exaggerating the effect of screening on incidence. As such if our study finds that non-screening is non-inferior to screening this finding could not be explained by this bias. In a sensitivity analysis, the numerator of the primary endpoint will only include diagnoses if there was a negative test result at the prior visit.

Because any positive Ng/Ct test from the test of cure visits is considered a non-resolved old infection, these will not be included in the primary or secondary outcomes as new infections. If however the test of cure was to assess if an Ng infection had cleared and a new Ct infection was detected at the test of cure visit then this would be included as a new infection in the primary and secondary study outcomes.

Secondary endpoints

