Interim analyses are planned at two time points: once 50% and 100% of all study recruits have passed their 6 month visit. For the first interim analysis, data is used of the first 507 enrolled participants (i.e. ordered by randomization date) until 6 months follow-up. For the second analysis, data is used of all enrolled participants until 6 months follow-up. The goal of the interim analyses (at both time points) is to estimate the incidence rate ratio of symptomatic Ng plus CT. Estimates will be based on a Poisson regression model (or a negative binomial regression model if there is overdispersion) with number of symptomatic diagnoses as dependent variable, arm and hospital as independent variables and log(number of visits) as offset. This model will provide estimates of the incidence rate in each arm and the incidence rate ratio (no screening versus screening), together with 95% confidence interval. Visits with missing data on the diagnosis of Ng or Ct, will be excluded from the calculation of the incidence rate (excluded both from numerator and denominator).

7. Analysis of main efficacy outcomes: Incidence of Ng plus Ct

In each arm, the incidence of Ng plus Ct will be estimated together with 95% confidence interval. Estimates will be based on a Poisson regression model (or a negative binomial regression model if there is overdispersion) with number of diagnoses as dependent variable, arm and hospital as independent variables, and log(number of visits) as offset. This model will also provide an estimate of the log incidence rate ratio (no screening versus screening), together with 95% confidence interval. The 'no screening' arm is proven to be non-inferior if the upper limit of the 95% confidence interval is lower than $\log(1.25)$.

Visits with missing data on the diagnosis of Ng or Ct, will be excluded from the calculation of the incidence rate (excluded both from numerator and denominator).

In a sensitivity analysis, the numerator of the primary endpoint will only include diagnoses if there was a negative test result at the prior visit.

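### A tested visit outside its window keeps its positive result in the numerator but leaves the denominator, so each arm's incidence is overstated; the non-inferiority ratio is not shown to be affected

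*SAP*

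**What the plan says.** Protocol 8.7 allows each 3-monthly visit from one week early to six weeks late. SAP 3 then sets the rule for visits outside that range: "Scheduled visits that were performed out of window (cfr. protocol) are considered as unscheduled visits, with the corresponding scheduled visit considered as" not done. For late visits this carries out protocol 11.3.4, which defines a visit more than six weeks late as missed and takes missed visits out of the denominator. For visits more than one week early it is new in the SAP.

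Four further rules meet this one:

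- **Numerator (SAP 5.2):** "Thus each participant can contribute up to 2 diagnoses (Ct/Ng) at each (scheduled or unscheduled) visit". Protocol 8.7 confirms that infections found at non-scheduled visits between 0 and 12 months enter the outcome.
- **Denominator (SAP 5.2):** "The denominator does not include unscheduled visits". SAP 7 uses log(number of visits) as the offset. The interim (SAP 6) and symptomatic (SAP 8.2) models have the same form: "arm and hospital as independent variables and log(number of visits) as offset".
- **Missing results (SAP 7 and 7.2):** a visit without an Ng/Ct result is "excluded both from numerator and denominator".
- **Per-protocol set (SAP Table 1):** "Fewer than three scheduled follow-up visits with Ng/Ct result available" is a major violation, and per-protocol is the primary approach.

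**The concern.** A planned test done outside the window is still a test, and its result is used if positive. The visit that produced it is not counted as exposure. The rule that drops both sides does not help, because it covers only visits without a result. The sensitivity analysis requiring a prior negative filters the numerator only.

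This also sits badly with the protocol's own reasoning. The footnote to protocol 4.3.1 bases the denominator on study visits that have Ng/Ct results, so that it tracks the chance of testing positive. A late planned visit with a result fits that purpose. Protocol 11.3.4 asks that participants who pass the window be contacted to attend as soon as possible, so late tested visits should be expected to occur.

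Two things are at stake: the per-arm incidences with 95% confidence intervals that SAP 7 plans to report, and membership of the primary PP set.

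**Working it through.** **Inputs.** Protocol 11.1 gives the diagnosis table, 0.72 diagnoses per four visits, 95% of participants with four tested visits and 5% with three, and N = 912 for 80% power. The out-of-window share f is not in the documents; every value below is an assumption. The 5% with three of four visits corresponds to 0.05 × 1/4 = 1.25% of visits. That describes visits without data, not late tested visits, so it is only a proxy.

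**The plan's own figures.** Rate per visit = 0.79×0.15 + 0.18×0.28 + 0.03×0.34 = 0.1791, or 0.716 per four visits (stated: 0.72). Simulating from the protocol's table with 912 participants and no out-of-window visits gives 80.2% power, so the stated sample size is reproduced.

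**One participant.** Four tested visits, one outside the window: results from four tests are divided by three visits, an inflation of 4/3.

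**ITT set.** With a constant event rate per tested visit and every out-of-window positive counted, inflation = 1/(1-f).

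**PP set.** Let Pn(k) be the binomial probability that k of n tested visits are outside the window. Participants stay in with at least three in-window tested visits.

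- Tested visits among those kept: 0.95×4×[P4(0)+P4(1)] + 0.05×3×P3(0)
- Counted visits among those kept: 0.95×[4×P4(0)+3×P4(1)] + 0.05×3×P3(0)
- At f = 10%: P4(0) = 0.6561, P4(1) = 0.2916, P3(0) = 0.729. The ratio is 3.711/3.434 = 1.081.

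**PP loss although tested three or four times.** If everyone has four tested visits, loss = 1 - P4(0) - P4(1); at f = 10% this is 5.23%. Adding the 5% with three visits: 0.95×0.0523 + 0.05×0.271 = 6.3%.

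| f (assumed) | ITT inflation | PP inflation | 0.72 would read (ITT / PP) | PP loss of 912 |
|---|---|---|---|---|
| 1.25% (proxy) | +1.3% | +1.2% | 0.73 / 0.73 | 0.1–0.3% (1–2) |
| 5% | +5.3% | +4.4% | 0.76 / 0.75 | 1.4–2.0% (13–19) |
| 10% | +11.1% | +8.1% | 0.80 / 0.78 | 5.2–6.3% (48–58) |

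The loss is zero if the protocol's 5% are exactly the participants with one recoded visit.

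**Month 12.** A recoded month-12 visit beyond its window falls after 12 months, so under protocol 8.7 its positive may not count. If every out-of-window month-12 visit is treated that way, inflation (ITT / PP) becomes +0.9% / +0.9%, +3.9% / +3.3% and +8.3% / +6.1%. This is a lower bound, because early month-12 visits still count.

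**Clustering.** If lateness clusters within participants (assumed correlation 0.2), f = 10% gives PP inflation of +5.0% and PP loss of 10.1% (92 of 912).

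**Rate ratio.** In ITT the factor on the ratio is (1-f in the screening arm)/(1-f in the no-screening arm), which is 1 at equal f. The simulated ratio stayed at 1.00 in both ITT and PP at every equal f tried.

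**The case against.** The strongest reply is that the trial's decision is untouched. Non-inferiority rests on the rate ratio against 1.25, and SAP 2.1 says that "participants will be followed up in an identical fashion including 3x3 screening". That stands. A reader might infer that the recode biases the non-inferiority test. It would do so only if f differed by arm: 10% without screening against 5% with it would multiply the ITT ratio by 0.95/0.90 = 1.06, and the reverse by 0.95. The documents give neither evidence nor a direction for such a difference.

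A reader might also infer that SAP 3 departs from the protocol without cause. It does not for late visits, where it follows protocol 11.3.4. Protocol 8.1.2 also wants standardised periods for comparing incidence, which is a plausible motive for enforcing windows.

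Size is a fair objection too. Protocol 11.3.4 describes adherence as high, helped by 3-monthly prescriptions, and expects the window to reduce missed visits. Nothing supports 5% or 10%.

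The endpoint already counts unscheduled and outside diagnoses without a visit in the denominator, and the protocol's footnote defends this. That stands for extra visits, which the footnote describes as a very small share. It does not carry over to a planned test, whose removal lowers the visit count below the number of planned tests done.

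Finally, someone with two of four visits outside the window has arguably not followed the protocol as planned, and remains in the ITT analysis. That is a defensible choice, but Table 1 lists no visit-window violation; the exclusion arises only indirectly. It would not repair the numerator either, since a PP participant may still have one recoded visit.

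**Conclusion.** The mismatch is real as written and should be corrected, but its weight is modest. Whenever a recoded positive counts, the per-arm incidences are overstated, by up to 1/(1-f) in ITT and somewhat less in PP, and participants with enough results can be lost from the primary set. With the proxy of 1.25% the effect is close to negligible; the larger figures depend wholly on assumed values of f. All figures assume the same positivity in and out of window, and all but the clustered ones assume that visits fall outside the window independently. The documents do not support a claim that the non-inferiority conclusion is biased.

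A separate minor point: SAP 5.1.1 says "The Intention-to-Treat analysis will include all randomized participants with at least one follow-up visit", so someone with follow-up but no counted visit has log(0) as offset. This is a gap in the ITT definition whatever the cause, and not an effect of SAP 3 alone.

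**What to change.** In SAP 3 and 5.2, treat the result and its visit alike:

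- Count each tested planned 3-monthly visit within the 0 to 12 month follow-up (including the month-12 window), in or out of its own window, once in the numerator, once in the denominator and offset, and once toward the three-visit PP rule, up to four per participant.
- For a month-12 visit beyond its window, count neither the result nor the visit.
- Add a sensitivity analysis restricted to in-window visits, with out-of-window results and visits dropped from both sides.
- Apply the same rule to the interim, symptomatic and subgroup analyses.
- Align protocol 11.3.4 so that, for the denominator, missed means no Ng/Ct result.
- State in SAP 5.1.1 how an ITT participant with no counted visit is handled.

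The cost is one derivation rule and a protocol clarification; only visit dates and results are needed. Visit intervals become slightly less uniform and the PP set slightly broader. In simulation the rate returns to 0.716–0.717 per four visits (0.715–0.717 in single arms). A small PP loss remains from late month-12 visits among participants with three tested visits: at most 0.05 × 0.75 × f, or 0.05%, 0.2% and 0.4% at f = 1.25%, 5% and 10% (about 0, 2 and 3 of 912).
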